1.0 Background & Rationale

Symptom burden is a challenge for patients receiving chemotherapy, with nausea/vomiting and anxiety being some of the most common symptoms causing distress. In particular, the burden experience by patients receiving hematopoietic stem cell transplant (HSCT) may far exceed symptom burden experienced by the general oncology population due to extremely high doses of chemotherapy. Hematopoietic stem cell transplant (HSCT), also call bone marrow transplant, is the process of infusing healthy stem cells into the human body to replace damaged cells caused by disease or cancer (“Stem Cell Transplantation”, n.d.). Prior to receiving a HSCT, patients must receive high doses of chemotherapy and/or radiation in order to help decrease the amount of damaged or cancerous cells in the body leaving room for the new cells to reach the bone marrow and grow into cancer free blood cells. Due to high doses of treatment patients receive prior to HSCT, greater than 90% are likely to experience emesis despite the use of anti-emetics (Faiman, 2016).

Chemo-induced nausea, vomiting, and retching (CINVR) is the most severe and interfering symptom experienced by patients (Stricker & Wesmiller, 2015) and affects treatment-related quality of life (Wood, Chapman, & Eilers, 2011). High dose conditioning regimens damage the gastrointestinal mucosa and activate brain receptors, causing impulses to increase heart rate, respiratory rate, and saliva to cause CINVR (Faiman, 2016). CINVR may be more severe in the

delayed phase for patients receiving HSCT, defined as 24 hours after chemotherapy and lasting up to 7 or more days (Flank, 2017). Anxiety and depression are also common symptoms (Seo et al., 2019), due to prolonged hospitalization (4 weeks or more) separating patients from the comfort of their home and social network. Additionally, HSCT may be anxiety provoking as a last-option treatment for some patients that have experienced several treatment failures and cancer relapse(s).

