2.2 Secondary Objective

- Evaluate patient satisfaction with aromatherapy at completion of study.
- Evaluate the antiemetic administration between **nausea/vomiting symptom** intervention and control groups during the 48-hour intervention time span.
- Evaluate the number and incidence of unit falls pre and post intervention.

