12.0 Statistical Considerations

SAS and/or R statistical packages will be used to analyze primary outcomes, secondary outcomes, and demographic sample data.

Primary Outcomes

Comparisons between the intervention and control groups for differences in the CINVR and anxiety tools will be analyzed using mixed-model ANOVA, with time (baseline, 24 hours, 48 hours) repeated within subject. Chi-square tests will be used to compare the groups for differences in the proportions of patients prescribed medications for nausea/vomiting or anxiety. Separate analyses will be performed for the two symptom groups. A two-sided 5% significance level will be used for all tests.

Sample size justification: With sample sizes of 50 patients within each symptom group, 25 intervention/25 control within each symptom group, the study will have 80% power to detect an effect size of 0.81 between intervention and control within each symptom group, based on a two-sample t-test calculation and a two-sided 5% significance level. The recruitment target will be 112 participants (56 per symptom group) to account for a 10% drop out rate.

Secondary Outcomes

Descriptive statistics will be used to analyze frequencies and percentages of the patient satisfaction questionnaire responses, documented antiemetic administration, and number of unit falls. The number of (1) total antiemetic medication doses and (2) doses for each individual medication (i.e., Ativan, promethazine) will be compared between the control and intervention groups for the nausea/vomiting symptom group. The percentage change for number of falls will be calculated by comparing number of falls 12 months prior to intervention implementation to 12 months during implementation.

Descriptive statistics will be used to summarize the demographics of the study sample (frequencies and percentages for categorical variables, means and standard deviations for continuous variables).

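### The only named test on medication use is a chi-square on patients *prescribed* medication, placed under Primary Outcomes; it does not measure the dose reduction the protocol expects, and the outcome is secondary elsewhere

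*Combined protocol and SAP*

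**What the plan says.** Under the Primary Outcomes subheading of section 12.0, after the mixed-model ANOVA for the symptom scales, the plan states: "Chi-square tests will be used to compare the groups for differences in the proportions of patients prescribed medications for nausea/vomiting or anxiety". It adds "Separate analyses will be performed for the two symptom groups" and "A two-sided 5% significance level will be used for all tests". The planned size is "25 intervention/25 control within each symptom group".

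Elsewhere the status and the variable differ:

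- Section 2.2 lists medication use as a secondary objective, beginning "Evaluate the antiemetic administration between". Section 3.2 lists it again as a secondary outcome measure. Both speak of drugs administered over the 48 hours.
- Section 3.1 gives two primary endpoints only: change in INVR and change in shortened SAI.
- Section 7.0 records, for the nausea/vomiting group, drug, dose, whether the order was scheduled or as-needed, and number of doses given. It expects that as-needed medication may be required less often with aromatherapy, and it leaves background medication uncontrolled.
- The Secondary Outcomes part of section 12.0 opens with descriptive statistics. It then says that total doses and doses of each drug will be compared between arms in the nausea/vomiting group. No test, estimate or interval is named.

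**The concern.** Three things are at stake.

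**Status.** In section 12.0 the subheadings are what mark an analysis as primary or secondary. The chi-square sits under the primary one, so a reader cannot tell how its result is to be weighed.

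**Variable.** Prescribed yes/no is not the quantity the protocol hopes to change. A patient who needs one as-needed dose instead of six is still a patient with a prescription. This holds at any prescribing rate.

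**Sensitivity.** If nearly everyone in the nausea/vomiting group has an antiemetic prescribed, the table has few patients in the not-prescribed column. The chi-square approximation is then doubtful and modest differences will usually be missed. A null result could be read as evidence that medication use did not change.

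**Working it through.** **1. The plan's own figure.** The stated calculation is "80% power to detect an effect size of 0.81 between intervention and control within each symptom group", by a two-sample t-test. The noncentral t distribution with n = 25 per arm, effect size 0.81 and two-sided 5% gives 80.1% power, so the figure reproduces. The recruitment statement, "The recruitment target will be 112 participants (56 per symptom group) to account for a 10% drop out rate", also reproduces: 50 / 0.9 = 55.6, rounded up to 56 per symptom group, and 2 × 56 = 112. Neither figure concerns proportions. The plan gives no rate or power for the chi-square.

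**2. Inputs for the check.** From section 12.0: 25 per arm, symptom groups analysed separately (so 50 patients per table), two-sided 5%. Assumed: the prescribing rate, which the documents do not give. The nearest figure, in section 1.0, is "greater than 90% are likely to experience emesis despite the use of anti-emetics". That is a rate of emesis, not of prescribing, so a range is used.

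**3. Expected counts.** With equal arms, the expected not-prescribed count per arm is n × (1 − pooled rate).

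| Pooled rate | 25 × (1 − rate) |
|---|---|
| 80% | 5.0 |
| 85% | 3.75 |
| 90% | 2.5 |
| 95% | 1.25 |
| 100% | 0 (test undefined) |

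Counts fall below 5 only when the rate exceeds 1 − 5/25 = 80%. With 28 per arm (56 / 2, no dropout) the threshold is 1 − 5/28 = 82%.

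**4. What a significant result needs.** Suppose all 25 controls are prescribed medication. With 21 of 25 in the intervention arm, the Pearson statistic is 50 × (25×4 − 0×21)² / (25 × 25 × 46 × 4) = 500,000 / 115,000 = 4.35, p = 0.037; Fisher's exact p = 0.110. At 20 of 25 Fisher gives p = 0.0502, and at 19 of 25 p = 0.022. So the intervention arm must fall to 21 or fewer (Pearson) or 19 or fewer (Fisher).

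**5. Exact power.** Power is the sum, over all pairs of counts from two binomials with n = 25, of the probability of each table with p < 0.05.

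| Control vs intervention | Pearson | Fisher |
|---|---|---|
| 100% vs 90% | 24% | 3% |
| 98% vs 88% | 24% | 5% |
| 95% vs 85% | 21% | 7% |
| 90% vs 80% | 17% | 9% |
| 70% vs 60% | 12% | 7% |
| 60% vs 50% | 13% | 8% |
| 98% vs 78% | 66% | 39% |
| 98% vs 68% | 90% | 78% |

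With both arms at 95%, the true type I error is 2.0% (Pearson) and 0.08% (Fisher). In that case the Pearson test is conservative and does not produce excess false positives.

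**6. Reading the table.** A 10-point difference is poorly detected at every starting rate shown, so the low power there comes mainly from 25 per arm. What a high prescribing rate adds is sparse cells. What the yes/no variable adds, at any rate, is blindness to dose reduction among patients who still have a prescription.

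**The case against.** A reader might infer that the test sits at a ceiling and cannot detect reduced use. The documents do not support that. They give no prescribing rate; the figure above 90% is for emesis and is attributed to treatment given before transplant, whereas study treatment starts on post-transplant day 4 to 8. A ceiling is plausible, because this group consists of patients who name nausea/vomiting as their most burdensome symptom and eight drugs count, whether scheduled or as-needed. It remains an assumption. A large fall in the proportion could be detected, as the 98% vs 68% row shows.

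A reader might also infer that medication use has been declared a primary endpoint. No sentence says so; the conflict comes from the subheading.

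Two further points are fair. The sentence does not define the variable, and a per-drug or as-needed-only proportion need not be near 100%. And section 12.0 already plans a dose-count comparison, so a null chi-square would not stand alone.

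These objections limit the point but do not remove it. The placement conflicts with sections 2.2, 3.1 and 3.2. Prescribed conflicts with administered. The dose comparison, which suits the hypothesis, has no test or interval, so the only named inferential test on medication use is the less suitable one.

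**Conclusion.** The point holds in a limited form. Two parts rest on the text alone: the chi-square is placed under Primary Outcomes against its secondary status elsewhere, and prescribed yes/no does not capture the fewer as-needed doses that section 7.0 anticipates.

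The third part is conditional. If prescribing in the nausea/vomiting group exceeds about 80%, expected not-prescribed counts are below 5 per arm and the chi-square approximation is doubtful. With 25 per arm, most modest differences would be missed: for a 10-point fall, power is at most 24% by Pearson and 9% by Fisher across the starting rates tabulated. The figures assume that the variable means any antiemetic prescribed and that 25 per arm are analysed.

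The primary endpoints and their sample size are unaffected. The change is worth making because it improves a stated analysis at almost no cost.

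**What to change.** In section 12.0:

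1. Move the medication comparison from Primary Outcomes to Secondary Outcomes, to agree with sections 2.2, 3.1 and 3.2.
2. In the nausea/vomiting group, replace the prescribed yes/no test with the dose comparison already planned. Define the outcome as doses administered over the 48 hours: total doses, and as-needed doses identified from the recorded order type.
3. Name the method, either a rank test or a count model, and report an estimate of the difference between arms with a 95% CI.
4. Keep any binary summary descriptive. If it is tested, define it from administered doses and use an exact test where cells are sparse, noting that this lowers power (24% to 5% in the 98% vs 88% case).

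The cost is a wording change in section 12.0. Section 7.0 already has doses and order type recorded, so no new data are needed. The downside is that the binary test is lost or demoted.

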2.0 Objective(s)

2.1 Primary Objective

The purpose of this study is to evaluate the efficacy of aromatherapy on symptoms of CINVR and anxiety for patients hospitalized for hematopoietic stem cell transplant. The primary aim will be to evaluate the effect of inhaled aromatherapy on CINVR and anxiety symptoms compared to control for 48 hours.

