3.0 Outcome Measures

3.1 Primary Outcome Measures

Chemotherapy-Induced Nausea, Vomiting and Retching (CINVR)

CINVR involves three distinct gastrointestinal symptoms (nausea, vomiting, retching) influenced by administration of chemotherapy. Nausea is expressed as an unpleasant

feeling in the throat/epigastrium that can result in expulsion of stomach content, known as vomiting (Rhodes VA, 2001). Retching is the effort to expel stomach contents without success (Rhodes VA, 2001). A review of CINVR instruments identified the Rhodes Index of Nausea, Vomiting and Retching (INVR) was the only instrument that separately assesses all three symptoms (Wood et al., 2011). The INVR will be used to measure CINVR and includes 8 Likert-type items on a 5-point scale, with evidence supporting reliability (Spearman correlation 0.87) and validity (Rhodes & McDaniel, 1999). Completion of the tool will occur at baseline, 24 hour, and 48 hours of intervention.

The primary endpoint for CINVR is the mean INVR score change from (1) baseline to 24 hours and (2) baseline to 48 hours. We anticipate a 30% reduction in the INVR mean score for participants randomized to the intervention group who indicated nausea/vomiting as primary symptom of concern.

Anxiety

Anxiety is excessive or persistent worry about aspects of life ("Understanding the Facts of Anxiety Disorders and Depression is the First Step," n.d.). Anxiety will be measured using a shortened version of Spielberger's State Anxiety Inventory (SAI). The original SAI contains 20 items to measure state anxiety and items are scored using a 4-point Likert-type scale (almost never-almost always) (Spielberger, Gorsuch, Lushene, Vagg, & Jacobs, 1983). The SAI instrument has good internal consistency (.86-.95), test-retest reliability (.65-.75) (Spielberger et al., 1983), and evidence supporting construct and concurrent validity (Spielberger et al., 1983). The shortened SAI retains 6 items (from the original 20) and has evidence supporting good internal reliability consistency (Cronbach's alpha .84) and strong construct validity (Abed, Hall, & Moser, 2011). Completion of the tool will occur at baseline, 24 hours, and 48 hours of intervention.

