The primary endpoint for anxiety is the mean shortened SAI score change from (1) baseline to 24 hours and (2) baseline to 48 hours. We anticipate a 30% reduction in the SAI mean score for participants randomized to the intervention group who indicated anxiety as their primary symptom of concern.

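### Each symptom group has two unranked primary time points (24 h and 48 h), and the plan does not say which test decides or which one the 80% power belongs to

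*Combined protocol and SAP*

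**What the plan says.** Section 3.1 (Primary Outcome Measures) sets the endpoint for the nausea/vomiting group: "The primary endpoint for CINVR is the mean INVR score change from (1) baseline to 24 hours and (2) baseline to 48 hours". For the anxiety group it says: "The primary endpoint for anxiety is the mean shortened SAI score change from (1) baseline to 24 hours and (2) baseline to 48 hours". Neither sentence ranks the two times or says whether one or both must show an effect.

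Section 12.0 (Statistical Considerations) compares the arms by a mixed-model ANOVA with baseline, 24 h and 48 h as repeated times, separately in each symptom group. It adds: "A two-sided 5% significance level will be used for all tests". No model term or contrast is named as the deciding one, and there is no hierarchy or multiplicity adjustment.

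The sample size paragraph of the same section says "the study will have 80% power to detect an effect size of 0.81 between intervention and control within each symptom group". The calculation behind this figure is for one t-test between two arms of 25, at the 5% level, and the paragraph does not say to which time point or contrast the 0.81 refers.

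Section 2.1 (Primary Objective) states the aim: "evaluate the effect of inhaled aromatherapy on CINVR and anxiety symptoms compared to control for 48 hours". That describes a period; it does not rank 48 h above 24 h.

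**The concern.** A three-time model yields an overall group effect, a group-by-time test and a separate arm contrast for each change. Section 3.1 points to the two changes, Section 12.0 to the model, and the sample size to a single t-test. These are different primary tests with different error and power.

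If either change may carry the claim, two tests at 5% give more than a 5% chance of a false claim in that symptom group. If both must succeed, error is at most 5% but power is below the 80% stated. If the rule stays open, it can be settled after the results are seen. That matters more here because Section 5.0 says participants cannot be blinded, and both instruments are self-reported.

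**Working it through.** **Inputs from the documents.** Section 12.0: 25 per arm in each symptom group, effect 0.81 SD, two-sided 5%, two-sample t-test, 10% dropout. Section 3.1: two changes per symptom group.

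**Assumed.** The correlation r between the 24 h and 48 h changes is not given, so a range is shown. Changes are taken as bivariate normal, with complete data and an unstructured covariance. The two model contrasts then match two-sample t-tests on the changes with 48 df. Where an effect is present it is 0.81 SD at both times unless stated otherwise.

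**Step 1: the plan's own figures.** Noncentrality is 0.81 × √(25/2) = 2.864. The critical value of t with 48 df is 2.011. Power is P(|T| > 2.011) = 80.1%, so the stated 80% reproduces. For dropout, 50/0.9 = 55.6, rounded up to 56 per symptom group and 112 in total, which also reproduces.

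**Step 2: either time counts.** The error is P(|T24| > 2.011 or |T48| > 2.011) under no effect. With independent tests it would be 1 − 0.95² = 9.75%. With correlated changes it is lower (simulation, table).

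**Step 3: both times required.** Error is at most 5%. Power is P(|T24| > 2.011 and |T48| > 2.011), by simulation.

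**Step 4: group-by-time test alone.** This is the two-df joint test of both changes: F = T² × 47/(2 × 48) on 2 and 47 df, where T² is Hotelling's statistic. It holds 5%. With equal effects the noncentrality is (25/2) × 0.81² × 2/(1 + r) = 16.40/(1 + r), which is 12.62, 10.94 and 9.65 at r = 0.3, 0.5 and 0.7.

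| r | Either time: error | Both times: power | Group-by-time alone: power (error 5%) |
|---|---|---|---|
| 0.3 | 9.5% | 67% | 87.8% |
| 0.5 | 9.1% | 68.8% | 82.5% |
| 0.7 | 8.4% | 71.4% | 77.3% |
| 0.8 | 7.8% | 72.9% | 74.8% |

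**Step 5: overall group effect.** Assume equal within-patient correlation ρ among the three scores, with 0.81 in SD units of the change. Averaging over all three times, baseline included, gives a standardised effect of (2/3) × 0.81 × √(2(1 − ρ)) / √((1 + 2ρ)/3). That is 0.875, 0.661 and 0.468 at ρ = 0.3, 0.5 and 0.7, with power 86%, 63% and 37%.

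**Step 6: one named contrast.** Error is 5% and power 80.1% with 25 per arm, provided 0.81 is in SD units of that contrast.

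**The case against.** The strongest defence is that Section 12.0 plans one repeated-measures model, not two t-tests. For change from baseline, the natural omnibus test in that model is group-by-time. It holds 5%, and at r = 0.5 it has 82.5% power, so on that reading the plan meets both targets. This stands as far as it goes: the either-time and both-times figures describe possible readings, not stated rules. But the plan does not name the group-by-time test, and at r = 0.7 its power is 77.3%.

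Stronger conclusions are tempting but not supported:

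- A reader might infer that the plan breaks its own 5% guarantee. Section 12.0 sets a level per test and never promises 5% per symptom group. What is missing is familywise control or a deciding rule.
- A reader might infer that the trial is underpowered. The sample size arithmetic is correct for a single test.
- A reader might count tests across both symptom groups and ask for adjustment over all of them. The groups are different patients with separate analyses and separate claims, so none is needed.
- A reader might count the chi-square medication tests as further primary tests, because they appear under Primary Outcomes in Section 12.0. Section 3.1 lists only the INVR and the shortened SAI as primary, so the placement may be layout. Those tests enter none of the figures here.

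**Conclusion.** The gap is real: the deciding test is not specified, and the 80% power is attached to no particular time point or contrast. Its size depends on the reading. Error per symptom group is about 9.5% to 7.8% (r = 0.3 to 0.8) if either time suffices, and power is about 69% to 71% (r = 0.5 to 0.7) if both are needed. There is no loss if one contrast is named. A sole group-by-time test meets both targets at r = 0.3 and 0.5 but has less than 80% power at 0.7.

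The documents therefore support saying that the plan does not secure both 5% error and 80% power. They do not support saying that it must miss either one. All figures beyond the 80.1% rest on assumed correlations, complete data, unstructured covariance and, for power in Steps 3 and 4, equal effects at both times. This should be corrected, and wording is enough.

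**What to change.** Before outcome data are analysed, amend Sections 3.1 and 12.0:

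1. Name one primary contrast per symptom group at two-sided 5%. An example is the arm difference in change from baseline to 48 h from the mixed model, using INVR in the nausea/vomiting group and the shortened SAI in the anxiety group.
2. Test the other time at 5% only if the first is significant.
3. State that the 0.81 SD and the 80% power refer to the named contrast.

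Choosing 48 h fits the aim in Section 2.1 but is not forced by it; the sponsor could rank 24 h first. One point bears on the choice: under Section 7.0 patients complete the 24 h measures on their own and the reminder visit takes place Monday to Friday only, whereas a team member prompts the 48 h measures in person.

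**Cost.** Wording only, with no added patients. The downside is that an effect seen only at the second-ranked time could not be claimed as primary. For example, if the effect fades to 0.40 SD by 48 h, a 48 h test has noncentrality 0.40 × √(25/2) = 1.414 and 28% power.

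**If both times must stay primary.** State Holm's procedure and restate the power. With 0.81 SD at both times and r = 0.5 to 0.7, it is about 76% for a named time and 85% to 82% for at least one.

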The study team initial visit will be at 0 hours (visit 1) and follow-up visits will be completed at 24 hours (visit 2) and 48 hours (visit 3). During visit 2 (Monday-Friday only), the study team will remind participating patients to complete their symptom journal, will answer any study-related questions, and will inquire about any aromatherapy side effects. During visit 3, a study team member will instruct the patient to complete the 48-hour symptom measures in the journal and will complete a brief intervention satisfaction questionnaire (Appendix C) with the patient (intervention group only). Patients will be provided a \$25 gift card to show appreciation for their time in the study. After symptom data collection is completed, a study team member will review and document antiemetic medication administration from the electronic medical record during the 48-hour intervention time frame. **Antiemetic administration will be captured on an Excel spreadsheet on a secure Microsoft Team for intervention and control participants in the nausea/vomiting symptom group. Included medications are scopolamine, lorazepam, promethazine, prochlorperazine, olanzapine, dexamethasone, Marinol, and ondansetron indicated for nausea/vomiting. Medication type, dose, order type (scheduled vs. PRN), and number of doses will be documented for antiemetics administered during the study timeframe.** Concomitant medications (e.g., antiemetic medications, steroids, benzodiazepines) will not be controlled as part of the study as the intent is not to alter standard practice for symptom treatment, but rather to provide an adjuvant to help reduce symptom burden. However, it is reasonable to expect that the need for PRN (available as needed) medications prescribed for nausea/vomiting or anxiety may be less in the treatment group compared to control during the 48 hours of inhaled aromatherapy. Because antiemetic and benzodiazepine medications may contribute to an increase in fall risk (Seppala et al., 2018; Wildes et al., 2018), we also plan to observe fall events during the study timeframe. Unit fall total numbers and incidence data will additionally be obtained from data reported to the National Database for Nurse Quality Indicators (NDNQI) for 12 months prior to implementation and 12 months during study implementation.

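### The planned antiemetic comparison counts total and per-drug doses and does not separate the as-needed (PRN) doses that the protocol expects aromatherapy to reduce

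*Combined protocol and SAP*

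**What the plan says.** Section 7.0 (Study Procedures) makes three relevant statements.

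- It sets an expectation for the treatment group over the 48 hours: "it is reasonable to expect that the need for PRN (available as needed) medications prescribed for nausea/vomiting or anxiety may be less".
- It lists what will be captured in the nausea/vomiting group: "Medication type, dose, order type (scheduled vs. PRN), and number of doses will be documented for antiemetics administered during the study timeframe".
- It says that concomitant medications "will not be controlled as part of the study as the intent is not to alter standard practice for symptom treatment".

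Section 12.0 (Statistical Considerations), under Secondary Outcomes, opens with a general statement: "Descriptive statistics will be used to analyze frequencies and percentages of the patient satisfaction questionnaire responses, documented antiemetic administration, and number of unit falls". It then names the antiemetic comparison. "The number of (1) total antiemetic medication doses and (2) doses for each individual medication" "will be compared between the control and intervention groups for the nausea/vomiting symptom group". Order type is not mentioned.

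The only other medication analysis is the chi-square test under Primary Outcomes in the same section, on "differences in the proportions of patients prescribed medications for nausea/vomiting or anxiety". It has no split by order type either, and it concerns prescription, not doses given.

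The objective in section 2.2 and the outcome in section 3.2 refer to antiemetic administration in general. Section 3.2 lists dose, route and frequency, but not order type.

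**The concern.** The protocol says which use of medication it expects to fall, collects the field that identifies it, and then plans no comparison on it. Scheduled doses follow a standing order, and the study does not set out to alter standard practice, so they may largely reflect the regimen and not the patient's relief over 48 hours. A count that adds them to PRN doses can make a fall in PRN use look small in percentage terms. It can also carry a chance difference in background regimen between two arms of about 25.

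The per-drug counts do not solve this. Section 7.0 records order type as a field separate from medication type, and nothing ties a drug to one order type.

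At stake is whether a secondary outcome can answer the question that the protocol raises. If the PRN split appears only after the data are seen, it will be a post hoc analysis.

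**Working it through.** **1. The plan's own figure.** Section 12.0 gives 25 per arm in each symptom group, effect size 0.81, two-sided 5% and 80% power. A two-sample t-test (noncentral t) gives 80.1%, and the detectable effect at 80% power is 0.809. Recruitment is 50 / (1 − 0.10) = 55.6, so 56 per group and 112 in all. These figures reproduce. They concern the primary outcomes; no figure is given for antiemetic doses.

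**2. Relative effect on total doses.** Let *s* be the PRN share of all antiemetic doses in the control arm and *f* the fractional fall in PRN doses, with scheduled doses unaffected. Then

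relative fall in total doses = *f* × *s*.

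The documents give neither quantity. Here *f* = 30% is an assumption; it borrows the size of the reduction that section 3.1 anticipates for the INVR score.

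| PRN share *s* | Fall in total doses |
|---|---|
| 100% | 30% |
| 75% | 22.5% |
| 50% | 15% |
| 25% | 7.5% |

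The absolute difference in mean doses is the same in expectation whether scheduled doses are included or not.

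**3. Standardised effect.** Let *r* be the SD of scheduled doses divided by the SD of PRN doses, and ρ their correlation across patients. With no effect on scheduled doses,

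*d*(total) = *d*(PRN) / √(1 + *r*² + 2ρ*r*).

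Assume *d*(PRN) = 0.81, so that a PRN-only t-test with 25 per arm would have 80% power. The plan names no such test; this is a yardstick only.

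| *r* | ρ | *d*(total) | Power |
|---|---|---|---|
| 0 | any | 0.81 | 80% |
| 0.5 | 0 | 0.72 | 71% |
| 1 | 0 | 0.57 | 51% |
| 2 | 0 | 0.36 | 24% |
| 1 | +0.3 | 0.50 | 41% |
| 1 | −0.3 | 0.69 | 66% |
| 1 | −0.5 | 0.81 | 80% |
| 0.5 | −0.5 | 0.94 | 90% |

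The loss is zero when *r*² + 2ρ*r* = 0, that is at ρ = −*r*/2, and becomes a gain below that. For example, with a PRN SD of 3 and a scheduled SD of 2 (both assumed), *r* = 2/3 and the break-even correlation is −1/3.

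**4. Chance imbalance in the background regimen.** The standard error of the between-arm difference in mean scheduled doses is SD × √(2/25). For assumed SDs of 2, 4 and 6 doses it is 0.57, 1.13 and 1.70 doses. A 30% fall from an assumed mean of 4 PRN doses is 0.30 × 4 = 1.2 doses. Over part of this range, chance imbalance alone is as large as the effect sought.

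**The case against.** The strongest reply is that the planned counts match the stated objective. Sections 2.2 and 3.2 ask about antiemetic administration, not PRN use, and total use is a defensible measure. The PRN sentence is an expectation placed in the procedures section. The outcome is secondary and mainly descriptive, and the plan says that the counts are compared without naming a test. The rule "A two-sided 5% significance level will be used for all tests" would apply only if one were used. Pooling is inferred from the absence of a split, and the promise to describe documented antiemetic administration could take in order type. All of this stands. It limits the weight of the point, but the PRN comparison is still not specified.

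Two stronger readings are tempting and are not supported.

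- A reader might infer that the expected effect is necessarily diluted and that power is lost. That is certain only on the relative scale, and only if scheduled doses are given and are unaffected. On the standardised scale it depends on spread and correlation that the documents do not give. A negative correlation is plausible if heavier scheduled cover reduces PRN requests.
- A reader might infer that PRN doses are the only part that can respond within 48 hours. No section says so. Concomitant medication is uncontrolled, so orders could change during that time.

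A PRN count also has weaknesses. Background cover can influence PRN need, so a regimen imbalance can distort PRN counts too. Section 5.0 says that participants cannot be blinded, and as-needed use may be open to expectation effects.

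**Conclusion.** The concern holds as a gap between a stated expectation and the planned comparison. Section 7.0 expects lower PRN need and records order type; section 12.0 compares only total and per-drug doses. Even read as pure description, those counts do not show whether PRN use fell.

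If scheduled doses are largely unaffected by the patch, the relative effect shrinks in proportion to the PRN share, for instance from 30% to 15% at a share of one half. The effect on power is conditional. From an assumed 80%, it runs from 24% (scheduled SD twice the PRN SD, no correlation) to 90% (scheduled SD half the PRN SD, correlation −0.5), with no change at several points between. Shares, SDs and correlations are all assumed.

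The point is modest in weight: it touches neither the primary outcomes nor the sample size. It is worth making because the remedy uses data already being collected.

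**What to change.** In sections 3.2 and 12.0, prespecify the number of PRN antiemetic doses administered per participant over the 48 hours, compared by arm in the nausea/vomiting group, as the comparison that addresses the expectation in section 7.0. Add order type to the items listed in section 3.2. Report scheduled doses by arm beside it, so that an imbalance in background regimen can be seen. Keep the total and per-drug counts.

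The cost is a change of wording; data collection, sample size and patient care are unaffected. It adds one secondary comparison, and the report should note that PRN use in unblinded participants may reflect expectation. The change does not reach the anxiety-medication part of the expectation, because the dose capture in section 7.0 covers antiemetics in the nausea/vomiting group only.
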